7.3.12.3 Timing of Disease Assessments

Uniform disease response assessments will occur initially at 10 weeks (D64) (± 3 days) after treatment start of blinatumomab and thereafter every 12 weeks (± 3 days). **The scan on Day 64 will be compared to the scan from screening. Any other scan thereafter will be compared to the scan that was done immediately before it.**

PET/CT should be performed until documented complete remission, PD, **or relapse** or 24 months after the first assessment. Response assessment will also be conducted at the time of treatment discontinuation due to clinically suspected disease progression **or relapse**. If PET scans and CT scans are done separately, they both must be within the ± 3 -day window and a maximum of 72 hours apart. If PET and CT are acquired on the same day, it is strongly recommended that PET is performed prior to the CT with IV contrast. Subjects who receive at least 1 full dose of pembrolizumab who discontinue from all study treatment in cycle 1, for whatever reason, shall undergo a PET/CT scan between 14 to 28 days after last pembrolizumab exposure.

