Appendix I. Response Assessment per the Lugano Classification 2014

Response and Site	PET-CT-Based Response	CT-Based Response
Complete	Complete metabolic response	Complete radiologic response (all of the following)
Lymph nodes and extralymphatic sites	Score 1, 2, or 3* with or without a residual mass on 5PS† It is recognized that in Waldeyer's ring or extranodal sites with high physiologic uptake or with activation within spleen or marrow (eg, with chemotherapy or myeloid colony-stimulating factors), uptake may be greater than normal mediastinum and/or liver. In this circumstance, complete metabolic response may be inferred if uptake at sites of initial involvement is no greater than surrounding normal tissue even if the tissue has high physiologic uptake	Target nodes/nodal masses must regress to \leq 1.5 cm in LDI No extralymphatic sites of disease
Nonmeasured lesion	Not applicable	Absent
Organ enlargement	Not applicable	Regress to normal
New lesions	None	None
Bone marrow	No evidence of FDG-avid disease in marrow	Normal by morphology; if indeterminate, IHC negative
Partial	Partial metabolic response	Partial remission (all of the following)
Lymph nodes and extralymphatic sites	Score 4 or 5† with reduced uptake compared with baseline and residual mass(es) of any size At interim, these findings suggest responding disease At end of treatment, these findings indicate residual disease	\geq 50% decrease in SPD of up to 6 target measurable nodes and extranodal sites When a lesion is too small to measure on CT, assign 5 mm \times 5 mm as the default value When no longer visible, 0 \times 0 mm For a node $>$ 5 mm \times 5 mm, but smaller than normal, use actual measurement for calculation
Nonmeasured lesions	Not applicable	Absent/normal, regressed, but no increase
Organ enlargement	Not applicable	Spleen must have regressed by $>$ 50% in length beyond normal
New lesions	None	None
Bone marrow	Residual uptake higher than uptake in normal marrow but reduced compared with baseline (diffuse uptake compatible with reactive changes from chemotherapy allowed). If there are persistent focal changes in the marrow in the context of a nodal response, consideration should be given to further evaluation with MRI or biopsy or an interval scan	Not applicable
No response or stable disease	No metabolic response	Stable disease

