Target nodes/nodal masses, extranodal lesions	Score 4 or 5 with no significant change in FDG uptake from baseline at interim or end of treatment	$<$ 50% decrease from baseline in SPD of up to 6 dominant, measurable nodes and extranodal sites; no criteria for progressive disease are met
Nonmeasured lesions	Not applicable	No increase consistent with progression
Organ enlargement	Not applicable	No increase consistent with progression
New lesions	None	None
Bone marrow	No change from baseline	Not applicable
Progressive disease	Progressive metabolic disease	Progressive disease requires at least 1 of the following PPD progression:
Individual target nodes/nodal masses	Score 4 or 5 with an increase in intensity of uptake from baseline and/or	An individual node/lesion must be abnormal with: LDI $>$ 1.5 cm and Increase by \geq 50% from PPD nadir and
Extranodal lesions	New FDG-avid foci consistent with lymphoma at interim or end-of-treatment assessment	An increase in LDI or SDI from nadir 0.5 cm for lesions \leq 2 cm 1.0 cm for lesions $>$ 2 cm In the setting of splenomegaly, the splenic length must increase by $>$ 50% of the extent of its prior increase beyond baseline (eg, a 15-cm spleen must increase to $>$ 16 cm). If no prior splenomegaly, must increase by at least 2 cm from baseline
Nonmeasured lesions	None	New or recurrent splenomegaly New or clear progression of preexisting nonmeasured lesions

(continued on following page)

Response and Site	PET-CT–Based Response	CT-Based Response
New lesions	New FDG-avid foci consistent with lymphoma rather than another etiology (eg, infection, inflammation). If uncertain regarding etiology of new lesions, biopsy or interval scan may be considered	Regrowth of previously resolved lesions A new node > 1.5 cm in any axis A new extranodal site > 1.0 cm in any axis; if < 1.0 cm in any axis, its presence must be unequivocal and must be attributable to lymphoma Assessable disease of any size unequivocally attributable to lymphoma
Bone marrow	New or recurrent FDG-avid foci	New or recurrent involvement

Abbreviations: 5PS, 5-point scale; CT, computed tomography; FDG, fluorodeoxyglucose; IHC, immunohistochemistry; LDI, longest transverse diameter of a lesion; MRI, magnetic resonance imaging; PET, positron emission tomography; PPD, cross product of the LDI and perpendicular diameter; SDI, shortest axis perpendicular to the LDI; SPD, sum of the product of the perpendicular diameters for multiple lesions.

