Appendix J. Revised Response Criteria for Malignant Lymphoma

Response	Definition	Nodal Masses	Spleen, Liver	Bone Marrow
CR	Disappearance of all evidence of disease	(a) FDG-avid or PET positive prior to therapy; mass of any size permitted if PET negative (b) Variably FDG-avid or PET negative; regression to normal size on CT	Not palpable, nodules disappeared	Infiltrate cleared on repeat biopsy; if indeterminate by morphology, immunohistochemistry should be negative
PR	Regression of measurable disease and no new sites	$\geq 50\%$ decrease in SPD of up to 6 largest dominant masses; no increase in size of other nodes (a) FDG-avid or PET positive prior to therapy; one or more PET positive at previously involved site (b) Variably FDG-avid or PET negative; regression on CT	$\geq 50\%$ decrease in SPD of nodules (for single nodule in greatest transverse diameter); no increase in size of liver or spleen	Irrelevant if positive prior to therapy; cell type should be specified
SD	Failure to attain CR/PR or PD	(a) FDG-avid or PET positive prior to therapy; PET positive at prior sites of disease and no new sites on CT or PET (b) Variably FDG-avid or PET negative; no change in size of previous lesions on CT		
Relapsed disease or PD	Any new lesion or increase by $\geq 50\%$ of previously involved sites from nadir	Appearance of a new lesion(s) > 1.5 cm in any axis, $\geq 50\%$ increase in SPD of more than one node, or $\geq 50\%$ increase in longest diameter of a previously identified node > 1 cm in short axis Lesions PET positive if FDG-avid lymphoma or PET positive prior to therapy	$> 50\%$ increase from nadir in the SPD of any previous lesions	New or recurrent involvement

Abbreviations: CR, complete remission; FDG, ^{18}F fluorodeoxyglucose; PET, positron emission tomography; CT, computed tomography; PR, partial remission; SPD, sum of the product of the diameters; SD, stable disease; PD, progressive disease.

Cheson et al, 2007

Amendment 6

Protocol Title: A Phase 1b Open Label Study Investigating the Safety and Efficacy of Blinatumomab in Combination With Pembrolizumab in Adult Subjects with Relapsed or Refractory Diffuse Large B-Cell Lymphoma (DLBCL)

Amgen Protocol Number (AMG 103/Blinatumomab) 20150290

Amendment Date: 16 March 2022

Rationale:

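### Protocol Section 7.3.12.3 compares every scan after Day 64 with the one before it, but the adopted response criteria refer to baseline or nadir

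*Protocol*

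**What the plan says.** Section 7.3.12.3 schedules the first response scan at Day 64 and later scans every 12 weeks. Day 64 is compared with screening. For all later scans the rule is: "Any other scan thereafter will be compared to the scan that was done immediately before it".

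Section 7.3.12.1 makes the Lugano Classification (Appendix I) the site's primary measure of response and the basis for disease-related management, and keeps the Revised Response Criteria (Appendix J) alongside it. Their reference points are:

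- Appendix I, PET partial response: a score of 4 or 5 "with reduced uptake compared with baseline and residual mass(es) of any size".
- Appendix I, PET progression: "Score 4 or 5 with an increase in intensity of uptake from baseline and/or" new FDG-avid foci.
- Appendix I, CT stable disease: less than a 50% "decrease from baseline in SPD of up to 6 dominant, measurable nodes and extranodal sites".
- Appendix I, CT node or lesion progression: a rise of at least "50% from PPD nadir", together with "An increase in LDI or SDI from nadir" of 0.5 cm (lesions up to 2 cm) or 1.0 cm (larger lesions).
- Appendix I, spleen: "If no prior splenomegaly, must increase by at least 2 cm from baseline". With prior splenomegaly, the rule refers to the earlier increase beyond baseline.
- Appendix J, relapse or progression: an increase of at least 50% "of previously involved sites from nadir". For its 50% SPD decrease, Appendix J names no reference scan.

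Protocol Section 10.1.1.2 and SAP 6.2 take progression for PFS and DOR from Lugano; SAP 6.2 adds versions by the Revised Response Criteria. SAP 6.2 names no reference scan.

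**The concern.** Two comparators are in force for the same scan. If a site follows the timing section, the category it records is not the one the appendices define. Sites apply the criteria, and Amendment 5 removed the central read, so no independent reading would show the difference.

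The recorded category feeds treatment-period objective response, PFS and DOR. It also feeds patient management: Section 6.2.3 ties discontinuation to documented progression and counts the first documented progression as the event even if treatment continues. A missed progression can therefore prolong treatment and lengthen PFS. An early call can end treatment and shorten PFS. Because the errors can run both ways, no single correction would repair the estimates afterwards.

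**Working it through.** The plan states no figure to reproduce. The check sets the comparators side by side and then tests whether the category changes. Thresholds and scan days come from the documents; the lesion paths and growth rates are assumptions chosen to illustrate.

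| Finding | Reference in the appendices | Section 7.3.12.3 after Day 64 |
|---|---|---|
| PET uptake: PR, no response, PD (App. I) | baseline | previous scan |
| CT 50% SPD threshold (App. I, stable-disease row) | baseline | previous scan |
| Splenic progression (App. I) | baseline | previous scan |
| CT node or lesion progression (App. I) | nadir | previous scan |
| Relapse or PD (App. J) | nadir | previous scan |

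**Size-based progression.** Take two nodes of 4.0 × 3.0 cm at nadir, with the product growing 30% per 12-week interval and the shape unchanged.

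- SPD: 2 × 12.0 = 24.0; × 1.30 = 31.2; × 1.30 = 40.56.
- From nadir: 40.56/24.0 − 1 = +69%. The longest diameter goes from 4.0 to 4.0 × 1.30 = 5.2 cm, which is +1.2 cm. Both parts of the Appendix I rule are met, as is the Appendix J size threshold.
- From the previous scan: 40.56/31.2 − 1 = +30%. The longest diameter goes from 4.0 × √1.30 = 4.56 to 5.2 cm, which is +0.64 cm. Neither threshold is met.

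At a steady growth rate g per interval, the nadir rule crosses 50% at the smallest k with (1+g)^k ≥ 1.5: k = 5 for 10%, 3 for 20%, 2 for 30%. The previous-scan rule sees only g, so any steady rate below 50% never crosses. The 50% threshold alone is not Appendix I progression. Over two intervals the diameter grows by the factor 1+g, so a node above 2 cm also needs a nadir diameter of at least 1.0/g cm: 3.33 cm at 30%, 2.5 cm at 40%.

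This error has one direction. The nadir is never larger than the previous scan, so a rise of 50% over the previous scan is at least 50% over nadir. Size-based node or lesion progression can be missed or delayed but not called early.

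**PET uptake.** Uptake 20 → 8 → 12, scored 4 or 5 throughout: 12/20 − 1 = −40% from baseline, so no uptake progression; 12/8 − 1 = +50% from the previous scan, so an early call.

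**Late partial response, CT-based Lugano.**

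- SPD 100 → 60 → 42: 1 − 42/100 = 58% below baseline (PR); 1 − 42/60 = 30% below the previous scan (stable).
- SPD 100 → 140 → 68, each node up 40% at first and so not progressed: 1 − 68/100 = 32% below baseline (stable); 1 − 68/140 = 51.4% below the previous scan (a false PR).

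**Spleen, CT-based Lugano, no prior splenomegaly.**

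- 11.0 → 12.0 → 13.0 cm: +2.0 cm from baseline (PD); +1.0 cm from the previous scan (missed).
- 12.5 → 10.2 → 12.4 cm: −0.1 cm from baseline; +2.2 cm from the previous scan (early).

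**Timing.** Scheduled scans fall on Days 64, 148, 232 and 316. Twelve weeks is Day 84, so the scheduled 12-week window holds only the Day 64 scan, which is compared with screening. For CT node or lesion progression, the rules can first differ at Day 148 if screening is the nadir, or at Day 232 if Day 64 is.

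**The case against.** The strongest reply is that the sentence sits in a section on timing and does not say that it sets the response category. Section 7.3.12.1 makes Lugano the primary measure, and Section 10.1.1.2 ties progression to it. A reader could view adjacent scans side by side and still categorise by the appendices. The Amendment 6 rationale lists no change of response criteria.

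That reading is possible but unlikely. The sentence is mandatory in form and is paired with the Day 64-against-screening rule, which is the response reference for that scan. A site would read both alike. Nothing limits the sentence to descriptive viewing. Section 7.3.12.4 does name another comparator, the scan that first showed progression, but only to decide whether treatment continues.

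Other parts of the reply do stand and limit the point:

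- A reader might infer that PET uptake progression can also be missed, for instance on 10 → 11 → 12 → 13. Appendix I gives no numeric cut-off, so the rise at Day 64 already counts. More generally, the first scan above baseline follows scans at or below it and so also exceeds the previous scan. A miss needs an assumed cut-off.
- The Lugano SPD, node-size and spleen examples belong to CT-based assessment, mainly lymphoma not FDG-avid at screening, for which PET need not be repeated. An FDG-avid subject with reduced uptake at score 4 or 5 is a PET partial response whatever the SPD. The Appendix J progression examples are not restricted in this way.
- A reader might suppose that a missed progression is caught at the next scan, 84 days later. Under steady growth below 50% per interval it would not be caught by size at any scheduled scan.

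**Conclusion.** The contradiction is plain on the face of the documents and should be fixed. Followed as written, Section 7.3.12.3 can miss or delay size-based progression (under Appendix J generally, under Appendix I in CT-based assessment), call PET uptake progression early, and in CT-based Lugano assessment miss or falsely call late partial response and miss or prematurely call splenic progression.

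Exposure is limited. SAP 11 records that Part 2 was not pursued, so the subjects concerned are a subset of at most 30 in Part 1: those still imaged after Day 64, mainly in partial response or stable disease, since scheduled PET/CT stops at documented complete remission or progression. How many were misclassified, if any, cannot be estimated. It depends on whether sites followed the sentence and when it took effect. The SAP is written to Amendment 5, and the sentence is in bold like the Amendment 6 additions, so it may be newer than the SAP's base version; that is an inference.

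A reader might go further and conclude that the primary endpoint or the headline response rate is compromised. The documents do not support that. DLTs, the scheduled 12-week ORR and CR, and the interim efficacy rule do not use the previous-scan comparison. New lesions, death and growth of the SPD or lesion product by 50% or more in one interval are also unaffected as far as the 50% rule goes.

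**What to change.** Replace the sentence in Section 7.3.12.3 with:

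> At every post-baseline assessment, response and progression are determined against the reference named in Appendices I and J: under Appendix I, screening (baseline) for PET uptake, the CT SPD decrease and splenic progression, normal size for splenic response, and nadir for CT node/lesion progression; under Appendix J, screening (baseline) for the SPD decrease and nadir for relapse/PD. The preceding scan may be viewed for context but does not set the category.

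Naming screening for the Appendix J SPD decrease fills a gap, since that appendix is silent. Leave the Section 7.3.12.4 comparator for treatment continuation unchanged. State the same references in SAP 6.2 for objective response, PFS and DOR.

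Ask sites whether any assessment after Day 64 was categorised by the previous-scan rule and, if so, re-categorise it from the existing scans. The query matters because new wording cannot correct scans already read.

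Cost: one protocol sentence with IRB/IEC approval of the amendment, one addition to SAP 6.2, and one site query covering at most 30 subjects. No new scans or patients are needed.

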7.3.12.4 Disease Assessments During the Trial

Immunotherapeutic agents such as pembrolizumab may produce antitumor effects by potentiating endogenous cancer-specific immune responses, which may be functionally anergic. The response patterns seen with such an approach may extend beyond the typical time course of responses seen with cytotoxic agents, and can manifest a clinical response after an initial increase in tumor burden or even the appearance of new lesions. Standard response assessment criteria may not provide a comprehensive response assessment of immunotherapeutic agents such as pembrolizumab.

In the setting where a subject's assessment shows unconfirmed PD/**relapse** by investigator assessment, study drug may be continued upon sponsor consultation if the

investigator considers the subject is clinically stable, and repeat imaging performed in 4-8 weeks from initial assessment suspicious for PD/**relapse**. Subjects that remain on treatment after the first suspicion of progression/**relapse** who then become clinically unstable are not required to have repeat imaging for confirmation.

Clinical Stability may be defined as:

- Absence of signs and symptoms (including worsening of laboratory values) indicating disease progression
- No decline in ECOG performance status
- Absence of rapid progression of disease or progressive tumor at critical anatomical sites (eg, cord compression) requiring urgent alternative medical intervention.

Imaging should also occur at any time when there is clinical suspicion of progression/**relapse**. If repeat imaging shows a reduction or stabilization in the tumor burden compared to the initial scan demonstrating PD, treatment may be continued/resumed. If repeat imaging confirms PD by investigator assessments, subjects will be discontinued from study therapy.

7.3.13 Laboratory Assessments

The analyses for all laboratory tests used throughout this study are listed in [Table 7-5](#). Bone marrow biopsy, lumbar puncture, chemistry, thyroid function tests, coagulation, hematology, IgG, urinalysis, creatinine clearance (CrCl), pregnancy tests, **and testing for Hepatitis B** will be performed locally. Anti-blinatumomab and anti-pembrolizumab antibodies, immune panel, serum cytokines, PK samples, core or incisional/excisional biopsy, and MRD by NGS will be evaluated centrally. Anti-pembrolizumab antibodies, pembrolizumab PK samples, thyroid function tests, chemistry, hematology/complete blood count (CBC), and urinalysis will be collected on the same day as pembrolizumab administration, which may be up to 3 days before or after each scheduled day from pembrolizumab cycle 2 onwards.

Amgen or the central laboratories will supply containers for sample collection, preparation, packaging and shipping. Detailed instructions for sample collection, processing, and shipping are provided in the central laboratory manual and/or Amgen-provided training materials. The date and time of sample collection will be recorded in the source documents at the site.

Blood draws should not be done via the central venous access. Exception: If a permanent central line with more than 1 lumen is used, blood draws can be done via the lumen that is not used for drug administration. Pharmacokinetic sample collection must

be from the opposite arm to that used for study drug infusion. If drug was administered via a central venous catheter, the PK sample collection should be from a peripheral site.

Table 7-5. Laboratory Assessments

Chemistry	Coagulation	Urinalysis	Hematology	Other Labs
Sodium	INR	Blood	Hemoglobin	Bone marrow
Potassium	Fibrinogen	Protein	Hematocrit	Lumbar Puncture ^a
Chloride	aPTT	Glucose	Reticulocytes	Anti-blinatumomab
Total protein			Platelets	Antibodies
Albumin			WBC	Anti-Pembrolizumab
Calcium			RBC	Antibodies
Magnesium			Differential	IgG
Phosphorus			•Neutrophils	PK (blinatumomab and pembrolizumab)
Glucose	Thyroid Function		•Bands/stabs	CSF analytes
BUN or Urea			•Eosinophils	Biomarkers
Creatinine	TSH		•Basophils	Pregnancy test
Uric acid	T3 or Free T3		•Lymphocytes	Serum Cytokines
Alkaline phosphatase	Free T4		•Monocytes	Immune panel
LDH				MRD by NGS
AST (SGOT)				HBs
ALT (SGPT)				HBc
C-reactive protein				
Amylase				
Lipase				
Bilirubin (total)				
GGT				

ALT = alanine aminotransferase; aPTT = activated partial thromboplastin time; AST = aspartate aminotransferase; BUN = blood urea nitrogen; CSF = cerebrospinal fluid; GGT = gamma-glutamyl transferase; IgG = immunoglobulin G; HBc = hepatitis B core; HBs = hepatitis b surface; INR = international normalized ratio; LDH = lactate dehydrogenase; MRD = minimal residual disease; NGS = next generation sequencing; PK = pharmacokinetic;; RBC = red blood cells; SGOT = serum glutamic oxaloacetate transaminase; SGPT = serum glutamate pyruvate transaminase; TSH = thyroid stimulating hormone; WBC = white blood cells.

^a Lumbar puncture only required if concerns of disease presence per investigator judgement

7.3.14 Pharmacokinetic Assessments

7.3.14.1 Blinatumomab

Pharmacokinetic (PK) assessments will be required for all subjects receiving blinatumomab.

In cohort Ia, blinatumomab samples will be collected at day 1 (predose, 4, 6, 8 h after start of 9 µg/d infusion), day 2 (any time), day 8 (6 - 10 h after start of 28 µg/d infusion), day 10 (any time), day 15 (1 hour after pembrolizumab infusion has ended in cohort Ia), day 22 (any time), day 29 (any time) and day 43 (any time) in cycle 1. In cohorts IIa and IIIa, blinatumomab samples will be collected on day 1 (predose, 4, 6, 8 hours after start of 9 µg/d infusion), day 2 (any time), day 8 (6 -10 hours after start of 28 µg/d infusion), day 10 (any time), day 15 (prior to start of 56 µg/d infusion in cohort IIa or 112 µg/d infusion in cohort IIIa and 2 hours and 6 hours after the start of infusion of blinatumomab), day 19 (1 hour after pembrolizumab infusion has ended), day 26 (any time), and day 40 (any time) in cycle 1.

In the expansion cohort, blinatumomab PK samples will be collected on day 2 (any time), day 10 (any time), day 22 (any time), and day 29 (any time) in cycle 1.

